ResearchSpace@Auckland

[figure not shown]
Suggested Reference

[name], [name], [name], & [name] (2013). Protocol for Sugar Babies Study. Protocol for clinical trial of dextrose gel for treatment of neonatal hypoglycaemia (The Sugar Babies trial).

Copyright

Items in ResearchSpace are protected by copyright, with all rights reserved, unless otherwise indicated. Previously published items are made available in accordance with the copyright policy of the publisher.

<https://researchspace.auckland.ac.nz/docs/uoa-docs/rights.htm>

The Sugar Babies Study Clinical Protocol

[name]
[name] [name]
[name] [name]
[name] [name]

Background

Neonatal hypoglycaemia (low blood sugar level) is a common problem and the only known common preventable cause of brain damage in the newborn period.^{1, 2} Hypoglycaemia is most common in the first twenty four hours after birth, and is a common reason for admission to the Newborn Intensive Care Unit. The exact incidence is difficult to establish due to the varying criteria used to screen for and define hypoglycaemia.³ There are groups of babies who are at greater risk of neonatal hypoglycaemia, including infants of diabetic mothers, growth restricted, small for gestational age (< 2500 g) and large for gestational age babies (> 4500 g).⁴⁻⁶

After a baby is born the blood glucose levels fluctuate as the baby adapts from continuous intravenous glucose supply from the placenta to the intermittent, fat-based enteral nutrient supply after birth. In clinical practice, blood glucose levels are measured in at-risk babies intermittently, commonly 3-4 hourly. However these intermittent blood tests may easily miss significant periods of low blood glucose levels, for example before feeds. Thus, it is possible that some infants with hypoglycaemia that may threaten brain function are not identified, or, alternatively, that some babies with only an occasional brief fall in blood glucose levels are at no risk of impaired brain function but are inappropriately and invasively treated. In diabetic patients, continuous monitoring of blood glucose levels can lead to improved metabolic control.⁷ Continuous glucose monitoring has been shown to be safe in preterm babies⁸ but its role in the management of neonatal hypoglycaemia has not yet been determined. The vast majority of neonatal hypoglycaemia is transient and is the result of delayed metabolic adaption following birth.

There has been controversy regarding the blood glucose level at which treatment should be provided to a baby. One of the reasons for the controversy is that it remains unclear how low the blood glucose level or for how long the blood glucose level needs to be below a certain value, before neurological damage occurs. Blood glucose levels below 2.6 mmol/l are generally accepted as requiring treatment.³ Blood glucose levels below 2.6 mmol/l may increase the likelihood of neurological damage.^{9, 10} However, once diagnosed, the best treatment for hypoglycaemia also remains unclear.

Current treatment choices vary depending on the baby's birthweight, gestational age, and associated risk factors. If the baby is able to feed, then initial treatment focuses on encouraging feeding. However, if the blood glucose level does not increase or the baby has difficulty with feeding then admission to the newborn intensive care unit is usually indicated. Standard clinical practice in the newborn intensive care unit can include breast feeds, additional feeding with infant formula, intravenous dextrose, or specific medications such as glucagon. However, ideal treatment would keep the mother and baby together wherever possible, optimise the establishment of breast feeding and support the metabolic transition.

There have been few studies investigating the best treatment for neonatal hypoglycaemia. Two studies performed in India aimed to prevent neonatal hypoglycaemia in both small- and large-for-gestation babies. All the babies were bottle fed and randomised to either receive standard formula or standard formula plus added powdered sugar (1.5 g added to each 30 ml formula). Both studies showed that with the additional carbohydrate the incidence of neonatal hypoglycaemia was significantly reduced.^{11, 12} However, formula feeding is not the most common or the preferred method of feeding babies in New Zealand.

If additional feeding does not reverse hypoglycaemia, intravenous dextrose is a common next standard treatment. A recommended regimen includes a bolus of 200 mg/kg of glucose (2 ml/kg of dextrose 10%) followed by an infusion of 8 mg/kg.min.¹³ This treatment has been shown to improve the blood glucose level without unnecessary hyperglycaemia.¹³

Another less commonly used treatment is 40% dextrose gel. Oral carbohydrate is first line treatment for low blood sugar levels in the conscious diabetic child or adult.¹⁴ However the Waikato Newborn Intensive Care Unit is the only unit in Australasia to use dextrose gel for the management of hypoglycaemia. The dextrose is absorbed across the buccal membranes and is reported to increase the blood glucose level and reduce the need for intravenous glucose infusion.¹⁵ The dose used (0.5 ml/kg or 200 mg/kg) is the same as that recommended for an intravenous bolus of dextrose.

Two studies regarding the use of dextrose gel have been reported in conference proceedings, although neither has been published in full. The first study was observational and reported using a dose of 0.5 ml/kg in 14 babies. There was a mean increase in blood glucose levels of 1.8 mmol/l twenty minutes after administration.¹⁶ The second study randomised 75 babies ≥ 36 weeks gestation who had blood glucose levels <2.5 mmol/l to either feeding or feeding plus 40% dextrose gel 1 ml/kg. The authors reported no differences in blood glucose levels in either group at 15 or 30 minutes after treatment. However, in bottle feed babies, the volume of the subsequent feed was significantly reduced after dextrose gel.¹⁷ Therefore, the role of dextrose gel in the management of hypoglycaemia remains unclear.

We therefore propose a randomised double blind placebo controlled trial to investigate the effectiveness of 40% dextrose gel as a treatment for hypoglycaemia in term and near term newborn infants.

Aim

To determine whether treatment with 40% dextrose gel is more effective than feeding alone in reversing neonatal hypoglycaemia in term and near term babies in the first 48 hours after birth.

Hypothesis

1. That 40% dextrose gel is more effective than feeding alone in reversing neonatal hypoglycaemia.
2. That intermittent blood glucose monitoring does not detect all episodes of hypoglycaemia.

Primary Outcome

Treatment failure, defined as a blood glucose level < 2.6 mmol/l 30 minutes after the second of two treatment attempts.

Secondary Outcomes

- The time taken to achieve an interstitial glucose level above 2.6 mmol/l for >1 hour.
- Incidence of recurrent hypoglycaemia (blood or interstitial glucose concentration <2.6 mmol/l) after initial successful treatment (defined as blood or interstitial glucose concentration > 2.6 mmol/l for >1 hour after initial treatment).
- Total duration of interstitial glucose levels < 2.6 mmol/l.
- Incidence of admission to the neonatal intensive care unit
- Frequency and total volume of formula administered in the first 48 hours
- Frequency and total volume of expressed breast milk administered in the first 48 hours
- Total dose of dextrose gel administered
- Incidence and total dose of intravenous dextrose administered in the first 48 hours
- Rate of full breast feeding at two weeks of age
- Mothers' experience of having a baby in the Sugar Babies Study

Study Design

Randomised, placebo controlled, double-blinded study in hypoglycaemic near-term and term babies, comparing the incidence of treatment failure in babies randomised to receive either 40% dextrose gel (BioMed New Zealand Limited), or a placebo vehicle gel (Carboxymethyl cellulose 2%).

Inclusion Criteria

- 35 weeks gestation or greater
- Age < 48 hours after birth
- Parental written informed consent

Exclusion Criteria

- Serious congenital malformations
- Terminal conditions
- Abnormalities of the skin or lesions which prevent application of the continuous glucose sensor monitor
- Prior administration of dextrose gel or medications for the management of neonatal hypoglycaemia
- Administration of intravenous dextrose or other treatments likely to affect blood glucose levels

Recruitment

Wherever possible at risk babies will be identified before birth and their parents invited to take part:

- Small for gestational age (estimated fetal weight <10th centile)
- Large for gestational age (estimated fetal weight > 90th centile)
- Estimated fetal weight < 2.5 kg or greater than > 4.5 kg
- Diabetic mothers

Additional at risk babies will be identified after birth including:

- Small for gestational age (birth weight <10th centile)
- Large for gestational age (birth weight > 90th centile)
- Birth weight < 2.5 kg or greater than > 4.5 kg
- Baby of diabetic mother
- Any baby thought to be at risk of hypoglycaemia for clinical reasons (eg not feeding well, possible symptoms)

Informed Consent

All parents identified before birth as expecting a baby at risk of hypoglycaemia will be provided with an information pamphlet in antenatal areas or delivery suite. After discussion with a member of the research team, written informed consent will be gained before birth whenever possible. When babies are identified after birth, a member of the research team will explain the study to the parents. After the parents have had time to consider the study, they will be asked for written informed consent. Parents may consent to take part in the study without giving consent for the continuous glucose sensor.

Methods

A continuous glucose sensor (CGMS® System Gold™, Medtronic, Minimed®, Northridge, USA) will be inserted as soon as feasible after consent is obtained. Where consent is obtained before birth, the sensor will be inserted in delivery suite immediately after birth. The sensor will be secured with a Tegaderm™ transparent dressing.

The mother and baby will be encouraged to have skin to skin contact and breast feed on demand, consistent with the current Waikato guidelines for the management of a baby following birth. If a baby is not interested in breast feeding the mother will be encouraged to express breast milk which will be given via syringe to the baby. Babies who are to be formula fed will be offered a feed (60 ml/kg.day).on day one of life, increasing to 90ml/kg on day two. Where possible the volume of the fed taken will be recorded.

It is routine clinical practice for babies identified as at risk of neonatal hypoglycaemia to have blood taken by heel prick at one hour of age for measurement of blood glucose levels.¹⁸

Babies who become hypoglycaemic, defined as a blood glucose level < 2.6 mmol/l, measured on a blood gas analyser or laboratory autoanalyser at more than one hour after birth, will be fed, and in addition will be randomised to receive 40% dextrose gel or an identical appearing placebo gel.

The randomisation will be done by computer randomisation using a balanced block design with a variable block size, and stratified by risk factors (infant of a diabetic mother, small for gestational age or < 2.5 kg, large for gestational age or > 4500 g, other).

The researcher will access the randomisation number from a Sugar Babies Study computer programme. The number will correspond with previously prepared numbered pack containing six identical syringes of gel. The researcher will administer 0.5ml/kg of gel from one syringe. The syringe and any remaining gel will be returned to the pharmacy at the completion of the study.

Babies will have the inside of the mouth dried with gauze square. The gel (0.5 ml/kg) will then be massaged into the buccal (inside of cheek) membrane. The baby will then be fed (breast or formula, according to the parents' choice).

The blood glucose will be measured again 30 minutes after treatment.

If the blood glucose level is > 2.6mmol/l then blood glucose level monitoring will continue according to the current clinical protocol (three pre-feed blood glucose levels in 24 h).

If the blood glucose level remains < 2.6 mmol/l the treatment will be repeated using another syringe from the allocated treatment pack, and the blood glucose level measured again 30 minutes later. If hypoglycaemia persists,

this will be considered a treatment failure, and the baby will be reviewed by either the Neonatal Nurse Practitioner or Doctor on call for the Newborn Unit. Frequently the baby will require admission to the Newborn Intensive Care Unit for ongoing management. Babies in the study who require admission to the newborn intensive care unit for management of hypoglycaemia will have additional 0.8 ml of blood taken at this time and stored for later measurement of alternative cerebral fuels. This blood sample will be taken prior to any treatment for the management of hypoglycaemia in the nursery. All babies admitted to the Newborn Intensive Care Unit will receive the standard clinical care for the management of hypoglycaemia. This will mean that some babies may receive dextrose gel 40% as part of the clinical care.

If the blood glucose level rises to >2.6mmol after the initial one or two doses of gel, then later falls below 2.6mmol/l again, the treatment will be repeated as described above, using a further one or two syringes from the allocated treatment pack. Not more than six doses of gel may be administered in 48 hours.

The continuous glucose monitor will remain in place for 48 hours or until the baby is no longer being treated for hypoglycaemia if this is more than 48 hours. The baby will be able to leave the hospital with the continuous glucose monitor *in-situ*. Both the parents and lead maternity care provider will be taught how to monitor the continuous glucose monitor insertion site, and how to enter data into the continuous glucose monitor.

At the completion of the study the continuous glucose sensor will be removed from the baby's thigh using a Cavilon™ wand to reduce the discomfort associated with the removal of the dressing. Any remaining gel and syringes will be returned to the Pharmacist.

Clinical concern

If there is clinical concern about the baby, the baby will be admitted to the Newborn Intensive Care Unit for on-going treatment.

Withdrawal from the study

A baby will be withdrawn from the study if a member of the research team or medical specialist considers it medically necessary, or if the parents wish to withdraw the baby from the study. In the event of this happening the reason for withdrawal will be recorded.

Power calculation

A pilot study identified 91 babies at risk of neonatal hypoglycaemia born at Waikato Hospital between 1st January, 2006 and 30th April, 2006. Of these babies 51 (56%) became hypoglycaemic, and 9 (20%) of these babies remained hypoglycaemic following two doses of dextrose gel. It is predicted that the failure rate with placebo gel will be higher and clinically important if it is greater than 35%. Using a one tailed design with alpha at 0.05 and beta at 0.2, the sample size required is 109 babies in each group. Allowing for a five

percent withdrawal rate the sample size is required to be 115 babies in each group.

Analysis

Data will be analysed on an intention-to-treat basis. Prespecified subgroup analyses will be according to reason for risk of hypoglycaemia (SGA, LGA, baby of diabetic mother, other) and intended primary mode of feeding (breast or formula). Additional adjustment will be made for pre-randomisation perinatal risk factors that are not balanced between groups.

Study time table

The Sugar Babies Study commenced November 13th 2008. We expect the study to run for three years in order to achieve the numbers required.

Significance

Hypoglycaemia is very common in the newborn period. It is the most common cause of preventable brain damage in the newborn period. The diagnosis and management remain controversial. The majority of babies are admitted to the Newborn Intensive Care Unit for treatment. We hope to determine the effectiveness of an oral carbohydrate treatment regimen that will reverse hypoglycaemia and allow the mother and baby to remain together. This may result in improving the rate of breast feeding and decrease hospital costs

Sugar Babies Study Personnel

Steering Committee

The purpose of the steering committee is to manage every aspect of the Sugar Babies Study.

Members of the Steering Committee

- [name]: Professor of Neonatology, Liggins Institute, University of Auckland,
- [name]: Neonatologist, Waikato District Health Board
- [name]: Neonatologist, Newborn Services, Auckland City Hospital
- [name]: Neonatal Nurse Practitioner, Waikato District Health Board, and PhD student, Liggins Institute, University of Auckland,

Data Monitoring Committee

Terms of Reference

The purpose of the Data Monitoring Committee is to review the accumulating data and determine whether the Sugar Babies Study should continue or be discontinued. The reasons for stopping the trial earlier than planned may include evidence of benefit, evidence of harm and/or evidence of futility.

Members of the Data Monitoring Committee:

- [name] (Chair) Professor of Obstetrics and Gynaecology, University of Adelaide
- Associate [name]: Associate [name], Liggins Institute, University of Auckland, and Neonatalogist, Newborn Services, Auckland City Hospital
- [name]: Paediatrician, Waikato District Health Board

The Data Monitoring Committee members are not study investigators nor have intellectual conflict of interests, which could impair his/her performance as part of the committee.

Meeting Schedule and Format

The Data Monitoring Committee will meet once, after 100 babies have been randomised.

Stopping Rules for Benefit

The standard stopping rules of O'Brien-Fleming will be used^{19, 20} i.e. if the difference between the treatment and control group for the primary outcome shows a one-sided difference at $p < 0.005$.

Stopping Rules for Harm

The standard stopping rules of Fixed Nominal (Pocock)^{20, 21} will be used i.e. if the difference between the treatment and control group for the primary outcome shows a one-sided difference at $p < 0.029$.

These stopping rules are provided as a guide for the Data Monitoring Committee. If the pre-determined statistical stopping boundary is crossed, the Data Monitoring Committee is required to make a wise judgement regarding whether to recommend stopping the Sugar Babies Study. This will be done after evaluation of the total evidence available and full assessment of the implications of stopping the study early.

The format of the meetings will be:

- Either by email correspondence, phone or face-to-face, as considered appropriate by the committee
- Confidential, between the Data Monitoring Committee members.

Extra open sessions can be arranged if the Data Monitoring Committee members require further information from the Steering Committee.

At these meetings, interim data analysis must remain confidential to the Data Monitoring Committee.

Interim Analysis

The pharmacist will be the only person who has access to the randomisation code. Therefore the pharmacist will prepare a report summarising the interim data of relevance to the Data Monitoring Committee. The report will identify the data only by groups A and B.

The researcher will inform the pharmacist of the primary outcome and any adverse events for each baby using the study number. The pharmacist will develop the Data Monitoring Committee report from these data (see attached draft report). If the Data Monitoring Committee is considering recommending changes or early termination of the study, further data may be requested.

Safety Monitoring Committee

Terms of Reference

The purpose of the Safety Monitoring Committee is to review adverse events that occur during the study and determine whether such events may be associated with the Sugar Babies Study.

Members of the Safety Monitoring Committee:

- Associate [name]: Associate Professor of Neonatology, Liggins Institute, University of Auckland, and Neonatologist, Newborn Services, Auckland City Hospital
- [name]: Paediatrician, Waikato District Health Board

Serious adverse events will be notified to the Safety Monitoring Committee by investigators within 48 hours of the event. The Safety Monitoring Committee will receive copies of all related documentation from the Investigators. The Safety Monitoring Committee is able to request further information as necessary.

Adverse events are to be reported to the Data Monitoring Committee.

Adverse events are:

Serious adverse events

- Death
- Seizures

Adverse events

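### Adjust the primary analysis for the qualifying blood glucose in every case, not only if it happens to be unbalanced

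*Protocol*

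**What the plan says.** Entry (Protocol, Methods): "Babies who become hypoglycaemic, defined as a blood glucose level < 2.6 mmol/l, measured on a blood gas analyser or laboratory autoanalyser", more than an hour after birth, are randomised. No confirmatory reading and no lower limit are stated.

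Outcome (Protocol, Primary Outcome): "Treatment failure, defined as a blood glucose level < 2.6 mmol/l 30 minutes after the second of two treatment attempts".

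Sequence (Protocol, Methods): "If the blood glucose level is > 2.6mmol/l then blood glucose level monitoring will continue according to the current clinical protocol". Otherwise, "If the blood glucose level remains < 2.6 mmol/l the treatment will be repeated using another syringe from the allocated treatment pack", with a further reading 30 minutes later. Failure thus needs the entry reading and two later readings all to be low, while one later reading is enough to clear the baby.

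Analysis (Protocol, Methods and Analysis): randomisation is stratified by risk factor only. The subgroups are reason for risk and intended feeding mode. The one covariate rule is extra adjustment for perinatal risk factors, present before randomisation, on which the arms turn out to differ. The qualifying glucose is not named as a stratum, subgroup or covariate.

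Sample size (Protocol, Power calculation): "9 (20%) of these babies remained hypoglycaemic following two doses of dextrose gel" in the pilot, a placebo failure rate of 35%, and "Using a one tailed design with alpha at 0.05 and beta at 0.2, the sample size required is 109 babies in each group".

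**The concern.** When entry and outcome use the same cut-off on the same measurement, the distance of the entry value below that cut-off matters for the outcome. A baby who qualified at 2.5 mmol/l is cleared by a change of 0.1; one who qualified at 1.5 needs a rise of 1.1. The Background section itself says that glucose fluctuates after birth and that most neonatal hypoglycaemia is transient, so some regression to the mean near 2.6 is to be expected in both arms.

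A baseline value that is known for every randomised baby and closely tied to the outcome is the covariate most worth fixing in advance. The stated rule works the other way: its trigger is observed imbalance, not prognostic strength, and it covers only perinatal risk factors. The choice of model then depends on the data, and the qualifying value may never enter. Precision and ease of interpretation are at stake, not the validity of the comparison.

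**Working it through.** **1. The plan's own figure.** Inputs from the Power calculation section: p1 = 0.20, p2 = 0.35, one-sided alpha 0.05 (z = 1.645), power 0.80 (z = 0.842). The mean rate is 0.275.

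n = [1.645 × √(2 × 0.275 × 0.725) + 0.842 × √(0.20 × 0.80 + 0.35 × 0.65)]² / 0.15² = [1.645 × 0.6315 + 0.842 × 0.6225]² / 0.0225 ≈ 108.5, so 109 per group (power 80.2%). Then 109 / 0.95 = 114.7, so 115. Both stated figures reproduce. (9/51 is 17.6%, not 20%. That is a separate matter, and 20% is used here as stated.)

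**2. Does the entry value matter when nothing truly changes?** Let T be a baby's true glucose and E = T + noise the entry reading; the baby enters if E < 2.6. Two later readings are T plus fresh noise, and the baby is cleared if either is at least 2.6. The documents give no SDs, so these are assumed. Share cleared by noise alone:

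| Noise SD (mmol/l) | 56% read below 2.6, between-baby SD 0.5 / 0.7 | T normal, mean 2.9, SD 0.5 |
|---|---|---|
| 0.1 | 11.8% / 8.5% | 19.7% |
| 0.2 | 22.6% / 16.5% | 36.3% |
| 0.3 | 31.8% / 24.1% | 48.6% |

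The 56% is the pilot's 51 of 91 babies. Using it as a single-reading rate is itself an assumption.

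Under the 56% assumption, at noise SD 0.2, about 51-52% of babies entering at 2.4-2.6 are cleared, about 19% of those entering at 2.0-2.4, and about 1% of those entering below 2.0. The level is uncertain, but the gradient with entry value is clear.

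**3. Does it still matter with a response to treatment?** Take T with mean 2.9 and SD 0.5, and noise SD 0.2. Add a response with mean μ and SD s after the first dose, and a further half-size response after the second. Set μ in each arm to give 35% and 20% failure. Failure rates, placebo v gel:

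| Response SD s | Entry above 2.4 | Entry 2.4 or below |
|---|---|---|
| 0.4 | 20.0% v 9.0% | 44.5% v 27.0% |
| 0.8 | 26.5% v 13.6% | 40.4% v 24.0% |

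Within placebo, the two entry bands differ by 44.5 − 20.0 = 24.5 points or 40.4 − 26.5 = 13.9 points. That is as large as, or larger than, the planned treatment difference of 15 points.

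**4. What does adjustment gain?** Trials of 109 per group were simulated and calibrated to 35% v 20%. Logistic regression was tested one-sided at 0.05, with and without E as a continuous covariate:

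| Between-baby / noise / response SD | Unadjusted | Adjusted |
|---|---|---|
| 0.5 / 0.2 / 0.5 | 81% | 86% |
| 0.5 / 0.3 / 0.3 | 81% | 86% |
| 0.6 / 0.2 / 0.7 | 81% | 85% |
| 0.5 / 0.2 / 0.4 (model of step 3) | 80.2% | 83.3% |
| 0.5 / 0.2 / 0.8 (model of step 3) | 81.9% | 83.4% |
| noise 0.2, response 1.0 | 79.6% | 81.4% |

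With 1,500 to 2,000 runs each, the Monte Carlo error of a power figure is about 1 point. Repeat runs of the first three settings gave gains of 4 to 7 points. The overall range is therefore about 1.5 (83.4 − 81.9) to 7 points, smallest where response varies most. For scale, going from 109 to 115 per group lifts the planned power from 80.2% to 82.0%, or 1.8 points.

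**The case against.** Several stronger readings are tempting, and the documents do not support them.

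- *The comparison is biased.* It is not: noise-driven clearance falls on both randomised arms alike.
- *The trial is too small.* If a share of babies cleared regardless of treatment and the planned rates left them out, power at 109 per group would fall, for example to 74.9% at a 10% share. But the 20% was seen after two doses and the 35% is set on the same outcome, so both plausibly already include such babies.
- *The outcome misses the aim.* The Aim section asks whether gel is better at reversing hypoglycaemia, which is defined by 2.6 mmol/l. Failure to get above that value answers it. The size of the rise is a different question.
- *Response is never confirmed.* Secondary outcomes cover sensor glucose held above 2.6 for over an hour, recurrence, and total time below 2.6. This cover is partial, since parents may decline the sensor.
- *The analysis ignores the entry value.* The protocol fixes no primary model and does not exclude this covariate.

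The best remaining objection is that covariate lists usually sit in an SAP, and none is shown here. Silence alone would indeed be no finding. But the Analysis section is not silent: it states a rule, triggered by imbalance and limited to perinatal factors, and that rule is a poor one for this outcome. It is also fair that the gain is small, rests on assumed SDs, and would take power above plan rather than repair a shortfall.

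**Conclusion.** The point holds as one of precision and prespecification. The shared cut-off makes the qualifying glucose a likely strong predictor of failure, and the stated adjustment rule would bring it in only by chance imbalance, if at all. The cost is about 1.5 to 7 points of power at the planned rates, for between-baby SD 0.5-0.6, noise SD 0.2-0.3 and response SD 0.3-1.0 mmol/l. These SDs are assumptions; other values would move the figure. The simulated gain is for the logistic test, and a test on the standardised risk difference is assumed to gain a similar amount. Validity, the 109 per group, the 80% power and the choice of primary outcome are not called into question.

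**What to change.** In the Analysis section, state that the primary analysis of treatment failure includes the qualifying blood glucose as a continuous covariate in every case, regardless of observed imbalance. Report a standardised (marginal) risk difference and risk ratio from that model, so that the result stays on the scale used for planning. For this covariate, the fixed choice replaces the imbalance trigger.

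Optionally, report blood glucose 30 minutes after the first dose, compared between arms with adjustment for the qualifying value, as a supportive description of the size of the rise. It reflects one dose, not the two-attempt strategy. No power gain should be claimed for it: its simulated power ran from 77% to 88% depending on how the second dose was modelled.

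The cost is a sentence or two of wording and, if the option is taken, one more secondary result. The primary outcome, treatment sequence, blood sampling and number of babies stay as they are.

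### The only covariate rule in the protocol selects adjustment factors by observed baseline imbalance; fixing the covariates in advance costs nothing and serves the trial better

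*Protocol*

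**What the plan says.** The Analysis section commits to intention to treat, to two sets of subgroup analyses, and to one rule on covariates: "Additional adjustment will be made for pre-randomisation perinatal risk factors that are not balanced between groups". It lists no candidate factors, gives no criterion for imbalance, and does not say whether the adjusted or the unadjusted result is primary.

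Under Methods, randomisation is "stratified by risk factors (infant of a diabetic mother, small for gestational age or < 2.5 kg", with two further strata: large for gestational age or above 4500 g, and other. The Analysis section uses these risk groups only for subgroups, by "reason for risk of hypoglycaemia (SGA, LGA, baby of diabetic mother, other". It names no model for the primary outcome. It neither includes the stratification factor in that model nor excludes it.

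**The concern.** After proper randomisation, a baseline difference between the groups is a chance event. Its size carries no information on whether the factor affects treatment failure, and that relation is what makes adjustment worthwhile. A rule triggered by imbalance can admit a weak factor that happens to differ and pass over a strong predictor that happens not to.

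Three things follow:

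- The adjusted model is known only once the baseline data have been seen.
- With no threshold and no primary analysis named, several models satisfy the sentence, and the choice among them is open.
- The stratification factor is the variable least likely to be picked, because the blocks within strata keep it balanced.

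This is not a detail left to a statistical analysis plan. The protocol states the selection method, and a later plan that followed it would inherit the weakness.

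**Working it through.** **The plan's own figure.** The Power calculation section gives "Using a one tailed design with alpha at 0.05 and beta at 0.2", a gel failure rate of 20% and a placebo failure rate of 35%. With pooled variance and no continuity correction, where the mean rate is 0.275:

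n = [1.645 × √(2 × 0.275 × 0.725) + 0.842 × √(0.20 × 0.80 + 0.35 × 0.65)]² / 0.15² = (1.0387 + 0.5239)² / 0.0225 = 108.5, so 109 per group.

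Allowing 5% withdrawal, 109 / 0.95 = 114.7, so 115. Both stated sizes reproduce; power at 109 per group is 80.2%. Nothing below changes them.

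**How often chance alone triggers the rule.** The protocol gives neither the number of factors nor a test, so assume k independent factors, each tested at 5%. The chance of at least one flag is 1 − 0.95^k:

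- k = 3: 14%
- k = 5: 23%
- k = 8: 34%
- k = 10: 40%

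A flag is not a harm in itself. These figures show only how often the adjusted model would be set by chance.

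**What the rule does to error and power.** Simulation used 218 babies, four strata in permuted blocks, logistic models, a one-sided 5% test and 3,000 runs per scenario. The remaining inputs are assumptions, because the protocol gives none:

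- Stratum shares of 40, 30, 15 and 15%.
- Stratum log-odds of −1.0, 0.3, 0.8 and 1.2, multiplied by 0.3, 0.6 or 1.0.
- Five independent covariates, each with a log-odds of 0.3 or 0.6 per SD.
- Failure of 27.5% in both groups under the null, and 20% against 35% under the alternative.

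Simulation error is about 0.4 points for type I error and 0.7 for power. Most favourable means the best of the unadjusted, the imbalance-adjusted and the five single-covariate models.

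| Stratum multiplier, covariate log-odds | Type I %: unadjusted / flagged only / most favourable | Power %: unadjusted / flagged only / strata / strata and all five |
|---|---|---|
| 0.3, 0.3 | 5.4 / 5.2 / 7.2 | 81.6 / 81.9 / 82.1 / 84.3 |
| 0.3, 0.6 | 5.3 / 5.0 / 8.2 | 79.3 / 79.9 / 80.0 / 86.9 |
| 0.6, 0.3 | 4.4 / 4.4 / 5.9 | 80.9 / 81.1 / 82.1 / 84.3 |
| 0.6, 0.6 | 5.0 / 4.7 / 7.5 | 81.3 / 81.8 / 82.5 / 89.9 |
| 1.0, 0.3 | 4.0 / 3.9 / 5.3 | 81.7 / 81.7 / 84.5 / 86.6 |
| 1.0, 0.6 | 3.8 / 3.3 / 6.0 | 81.7 / 82.2 / 83.9 / 91.1 |

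- At least one covariate was flagged in 22-24% of runs, in line with the 23% above.
- Adjusting only for flagged covariates kept type I error at 3.3-5.2% and added at most 0.6 power points to the unadjusted test.
- Reporting the most favourable model gave a type I error of 5.3-8.2%.
- Adding the strata gained 0.5-2.8 power points. Where strata were strongly prognostic, the unadjusted test was itself conservative (3.8-4.0%), and part of the gain is recovery from that.
- The model with strata and all five covariates had a type I error of 4.7-6.1%, so a little of its power gain is not free. This favours a short covariate list.

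**Qualifying glucose.** A separate simulation (2,000 trials per scenario, 109 per group, 35% against 20%, one-sided 5%) assumed an odds ratio per SD of 1.5, 2.0 or 2.5. Power rose from 80.8 to 81.8%, from 80.6 to 83.3% and from 81.2 to 86.5%, a gain of 1.0, 2.7 and 5.3 points. All randomised babies have values below 2.6 mmol/l, so the true strength within that range is unknown.

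**Subgroup labels against strata.** The strata join centile and weight with an or. The Recruitment section lists below the 10th centile and below 2.5 kg as separate criteria. The Background glosses small and large for gestational age by weight alone (below 2500 g, above 4500 g). The Analysis section uses bare abbreviations. A baby under 2.5 kg but above the 10th centile is in the small stratum. Read by centile, the same baby falls outside the SGA subgroup; read by the Background gloss or as shorthand for the stratum, inside it.

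**The case against.** The strongest reply is that the sentence is a modest secondary provision. It limits candidates to perinatal risk factors, a class chosen for presumed relevance. Its first word suggests that it adds to some other analysis, and nothing in it forbids adjusting for balanced predictors. Applied mechanically it does no measurable harm to type I error. All of this stands, and it bounds the point.

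Three stronger readings are tempting, and the document supports none of them:

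- **The stratification is dropped from the analysis and precision is lost.** The protocol is silent on the primary model. Silence is not exclusion, and model terms are commonly set in an analysis plan, which is not at hand. Any loss is conditional on the strata being omitted.
- **The rule leaves no control of the error rate.** The simulation shows control near nominal when the rule is followed as a fixed procedure. Inflation needs selective reporting, which the protocol does not propose, although it does not close it off.
- **The subgroups misclassify babies relative to the strata.** The four labels correspond one for one with the four strata, and shorthand is a natural reading. This is an ambiguity, not a demonstrated error.

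It is also fair that an unadjusted primary comparison would be valid, and that the choice of effect measure is a preference that the correction does not need.

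What survives is that the one selection rule the document states uses the wrong criterion and leaves its terms undefined.

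**Conclusion.** The point holds in limited form. The stated rule picks covariates by chance imbalance instead of prognostic value, leaves the model open, and returns almost nothing in precision (at most 0.6 power points in the scenarios run). It would tend to miss the stratification factor. It does not threaten the validity of the primary comparison: one-sided type I error was about 3-5% when the rule was applied mechanically, and about 5-8% only if the most favourable model is reported.

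Replacing the rule brings a modest expected gain, about 0.5-3 power points for the strata and about 1-5 for the qualifying glucose. Both figures rest on assumed prognostic strengths and stratum shares, and the first applies only if the strata would otherwise be left out. The sample size is unaffected. This is a free improvement.

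**What to change.** Replace the sentence on imbalance in the Analysis section with:

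*The adjusted analysis of the primary outcome includes the randomisation stratum and the qualifying blood glucose concentration, fixed before unblinding; the unadjusted comparison is reported alongside, and which of the two is primary is stated in advance. Observed baseline imbalance does not determine the covariates.*

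Define the risk-factor subgroups as the four randomisation strata, so that a baby under 2.5 kg but above the 10th centile is classified the same way in both.

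The cost is wording only. Both covariates are known before allocation, since a qualifying glucose and a stratum are needed to randomise a baby, and the size stays at 109 (115) per group.
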